1.4. Insomnia

Genome Wide Association Studies have demonstrated a strong correlation of the genetic risk of insomnia with depression and anxiety (36,37). Furthermore, insomnia has been identified as a primary risk factor for the onset, persistence and relapse of anxiety, depression and PTSD. In a Network Outcome Analysis of 768 individuals without history of depression, *difficulty initiating sleep* was one of only five direct predictors of first-onset major depressive disorder after six years follow-up (38).

Depending on the study methods, in long COVID patients the prevalence of clinically relevant insomnia was estimated between 5% (diagnosis of insomnia disorder in electronic medical records <6m following infection) and 24% (self-rated insomnia symptoms above clinical cut-off at 3-month follow-up). These symptoms could represent an important risk factor in the subsequent development of anxiety and depressive disorders, and a key mechanism underlying cognitive deficits.

2. Research Objectives

- 1) Describe the standardized evaluation of the psychopathological and neurocognitive function of long COVID NP patients and their evolution over time;
- 2) Explore the cross-sectional and longitudinal association between long COVID NP symptoms and immunological measures;
- 3) Define the prevalence and clinical characteristics of insomnia in long COVID NP patients, as well as its correlation to the clinical psychiatric and neurocognitive symptom domains;
- 4) Compare the immunological profile of long COVID NP patients to those of existing cohorts of comparable primary psychiatric conditions and healthy controls;
- 5) To examine the neuro-endocrine (HPA-axis) characteristics of long COVID syndrome

3. Methodology

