3.4. Endpoint measurements

“NP symptoms”

- Baseline and follow-up scores on clinical scales of depression, anxiety, and insomnia
- (subgroup) Baseline and follow-up cognitive functioning

“Inflammation”

- Quantitative measurement of HERV-W-ENV in serum at baseline
- Calculation of systemic immune inflammatory index (SII= thrombocyte count x neutrophile count / lymphocyte count) at baseline and follow-up
- Quantitative analysis of CRP and IL-6 at baseline and follow-up
- Quantitative analysis of kynurenine metabolites at baseline and follow-up

(subgroup) *“HPA axis”*

- CAR

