3.5. Statistical analysis

CAPRI has ongoing collaborations with StatUA and BIOMINA for statistical analyses of past and ongoing projects involving biomarker-data. In this project, we will study cross-sectional and bidirectional longitudinal associations between *NP symptoms* and *Inflammation* or *Insomnia* (cfr above).

To study the cross-sectional association using all available data, we will stack data from all timepoints in one cross-sectional dataset. To account for the fact that one person can have multiple observations in this combined cross-sectional dataset, we will analyze the association between NP symptoms and inflammation / insomnia (measured at the same timepoint) using linear mixed models with timepoint as repeated effect and patient identifier as within-subject effect and using an unstructured correlation matrix. Estimates from this model thus represent the cross-sectional association between predictor and outcome.

For longitudinal analyses the effect of baseline *Inflammation* and *Insomnia* on *NP symptoms* at 3- and 6-month follow-up will be evaluated using linear mixed models with time as repeated effect and patient identifier as within-subject effect and using an unstructured correlation matrix. Baseline predictor by time interaction (time coded as 0, 3, or 6) will be included to test differences in slope but retained only in models when statistically significant. Treatment group (antidepressant treatment, insomnia treatment, cognitive remediation, a combination, or none) will be included

as predictor. Baseline values of NP symptoms will be included as covariates, and all other covariates measured at baseline as well.

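### The longitudinal slope test is not adjusted for baseline symptoms: only the predictor, not the baseline NP score, gets a time interaction

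*Combined protocol and SAP*

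**What the plan says.** Section 3.5 (Statistical analysis) describes the longitudinal model. The predictors are inflammation and insomnia as measured at baseline. Their relation to later symptom scores "at 3- and 6-month follow-up will be evaluated using linear mixed models with time as repeated effect", with patient as the within-subject factor and "using an unstructured correlation matrix". One interaction with time is named: "Baseline predictor by time interaction (time coded as 0, 3, or 6) will be included to test differences in slope". It is "retained only in models when statistically significant". On adjustment the section says: "Baseline values of NP symptoms will be included as covariates, and all other covariates measured at baseline as well". It gives no interaction between the baseline NP score and time, and it does not rule one out.

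Section 3.4 defines the symptom endpoints as "Baseline and follow-up scores on clinical scales of depression, anxiety, and insomnia", plus cognitive functioning in a subgroup. Section 1.4 gives the reason to expect insomnia and symptoms to be related: "insomnia has been identified as a primary risk factor for the onset, persistence and relapse of anxiety, depression and PTSD".

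**The concern.** The plan adjusts for baseline symptoms, so a reader will take the slope test as asking whether the effect of insomnia or inflammation changes over follow-up among patients with the same baseline symptoms. The model as written does not answer that. A baseline score commonly predicts a near visit better than a later one, and a single common slope has no room for this. The unstructured covariance lets residual correlation vary with lag, but not the baseline slope. What is left over can only go into the one term allowed to vary with time, that of the predictor.

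The error can go either way: an apparent change in effect where there is none, or a real growing effect that is masked. The retention rule adds to this, because spurious interactions that reach significance are the ones kept.

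**Working it through.** The plan gives no figure for this model. Its one computed sample size (64, for a MANOVA) does not concern it.

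**Inputs from the documents.** Outcomes at months 3 and 6, unstructured covariance and a single time interaction (section 3.5). 50 patients (section 3.1), or 50 + 50 = 100 if the Ca controls are analysed with them.

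**Assumed inputs.** The documents give neither the predictor-baseline correlation r nor the slopes b3 and b6 of symptoms on the baseline score. They are varied below, with all variables in SD units.

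**Step 1: what the coefficient estimates.** As written, with X the predictor and Y0 the baseline score:

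Y3 = a3 + c3·X + b·Y0 + e3

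Y6 = a6 + c6·X + b·Y0 + e6

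Subtracting gives Y6 - Y3 = (a6 - a3) + (c6 - c3)·X + (e6 - e3). The term b·Y0 cancels. The unstructured covariance leaves the regression of Y3 on the difference free, so that part of the likelihood says nothing about c6 - c3. With complete data, the predictor-by-time estimate is therefore the simple regression of change on X. Simulated fits agree with that regression to about 1e-15.

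**Step 2: bias when the predictor has no effect given Y0.** If Y_t = b_t·Y0 + e_t and corr(X, Y0) = r, the coefficient has expectation r × (b6 - b3). With r = 0.5 and slopes 0.7 and 0.5: 0.5 × (0.5 - 0.7) = -0.10 SD over the three months. Coded per month this is -0.10/3 = -0.033; the test is the same.

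**Step 3: approximate rejection rate by hand.** Take a month 3 to month 6 correlation of 0.7. The variance of change is 1 + 1 - 2 × 0.7 = 0.60. Less the part explained by X, 0.10² = 0.01, this is 0.59. The standard error at n = 50 is about √(0.59/47) = 0.112, and 0.10/0.112 = 0.89. A two-sided 5% t-test on 48 degrees of freedom then rejects in about 14%.

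**Step 4: simulation** (residual correlation 0.5, no predictor effect, 1,000 to 2,000 datasets per row, simulation error about 0.7 points). Rejection at nominal 5%:

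| r | b3, b6 | r × (b6 - b3) | n=50 as written | n=50 with baseline by visit | n=100 as written | n=100 with baseline by visit |
|---|---|---|---|---|---|---|
| 0 | 0.7, 0.5 | 0 | 5.1% | 4.3% | 4.9% | 3.7% |
| 0.5 | 0.6, 0.6 | 0 | 4.9% | 5.0% | 4.8% | 4.9% |
| 0.15 | 0.7, 0.5 | -0.03 | 6.0% | 4.2% | 7.0% | 3.8% |
| 0.3 | 0.7, 0.5 | -0.06 | 8.4% | 4.6% | 10.7% | 5.8% |
| 0.5 | 0.7, 0.6 | -0.05 | 7.4% | 4.7% | 9.2% | 4.3% |
| 0.5 | 0.7, 0.5 | -0.10 | 13.6% | 4.1% | 22.9% | 5.7% |
| 0.5 | 0.8, 0.5 | -0.15 | 22.1% | 4.9% | 42.8% | 5.2% |

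Separate runs of the sixth row at n = 50 gave about 12 to 14%. A larger sample makes the test worse, because the bias stays while the standard error shrinks.

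**Step 5: masking.** At r = 0.5 and slopes 0.7 and 0.5, a true rise in the predictor effect from 0.05 to 0.20 SD (+0.15) is estimated as 0.15 - 0.10 = +0.05. Power at n = 50 is 7% as written and 21% with the added term.

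**Step 6: the model without the interaction.** With the predictor-by-time term dropped, the mean predictor effect was 0.002 (5.5% rejection) at r = 0.5 and 0.000 (5.7%) at r = 0.3. No bias is seen there.

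**The case against.** The strongest reply is that bias presupposes a question. If the slope test asks only whether symptom trajectories differ by baseline insomnia, then in the scenarios above they do differ, by r × (b6 - b3), and the 13.6% is power, not error. That is correct as algebra. But section 3.5 puts baseline symptoms in the same model, so the conditional reading is the natural one, and nothing in the section says that the adjustment does not reach the slope test. If the unadjusted question is meant, the plan should say so.

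Several other objections stand and limit the point:

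- The common slope is read from silence. It is how the text would ordinarily be programmed, not something the plan declares.
- The size is assumed. The statement in section 1.4 that "Genome Wide Association Studies have demonstrated a strong correlation of the genetic risk of insomnia with depression and anxiety" concerns genetic risk and gives no correlation between scale scores in this cohort.
- The coding of time as 0, 3 or 6 leaves open whether baseline rows are outcomes. If they are, the baseline score is regressed on itself, the fit is near-singular, and adding baseline by visit does not cure it. Indicative rejection at n = 50 is then 9.3%, 17.8% and 40.8% for r = 0.15, 0.3 and 0.5.
- Section 3.3.6 gives one follow-up cognitive assessment, at 6 months, so a follow-up-only model for cognition has no time interaction to estimate.

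A reader might also blame the general fall in symptoms over time. The time effect absorbs a falling mean. The mechanism is the weakening prediction by the baseline score.

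**Conclusion.** The point holds for the predictor-by-time test on the symptom scales with outcomes at months 3 and 6. The baseline adjustment does not reach that coefficient, which has expectation r × (b6 - b3) when the predictor has no effect given baseline symptoms. It is material if r is near 0.5 and the baseline slope falls by about 0.2 (bias about -0.10 SD, rejection about 12 to 14% at n = 50 and 22 to 23% at n = 100). It is small if r is 0.15 to 0.3 or the slope falls by only 0.1 (about 5 to 8% at n = 50). It vanishes if r = 0 or the two slopes are equal. The identity is exact for complete data.

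A reader might infer that the whole longitudinal analysis of insomnia and inflammation is biased, or that every predictor has an inflated error rate. The documents support neither. The average predictor effect is unaffected when the interaction is not in the model. Immune markers weakly related to baseline symptoms stay near nominal. The documents fix neither r nor the slopes. This is a defect in one test, cheap to remove, and worth removing before the data are analysed.

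**What to change.** In section 3.5:

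1. State that the outcome rows are months 3 and 6 only, with time coded 3 and 6 and the baseline score used only as a covariate.
2. Add the interaction of baseline NP score with visit to each symptom-scale model that contains predictor-by-time, and keep it regardless of significance. Cognitive outcomes, with a single follow-up, are excluded.
3. If time-0 rows are to stay as outcomes, remove the baseline score as a covariate instead, and describe the interaction as an unadjusted difference in trajectories.

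The cost is a few sentences, one degree of freedom per model and some precision for the interaction; no new data are needed. At r = 0.5 and slopes 0.7 and 0.5, with the Step 3 variances, the residual variance of change falls to 0.60 - 0.2² = 0.56, but the correlation with baseline divides the information by 1/(1 - 0.25). The standard error becomes about √(0.56/(46 × 0.75)) = 0.127 against 0.112, roughly 14% larger. At r = 0.3 it is √(0.56/(46 × 0.91)) = 0.116 against √((0.60 - 0.06²)/47) = 0.113, about 3% larger.

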3.1. Recruitment and study population

Inclusion criteria - patients:

All patients 18-70 years referred to the University Psychiatric Hospital (Campus UZA and Campus Duffel) for psychological and/or cognitive complaints at least >4 weeks following a confirmed diagnosis of COVID-19 infection with a positive PCR test or an antibodies test will be invited to participate in the study. The sample size of the patients is estimated on 50 participants. **The patients have to be examined by their**

treating physician before enrollment to make sure other medical causes for their complaints are excluded. A positive score on at least two domains (psychological / cognitive) is necessary during the screening phase (see 3.3.1).

Inclusion criteria – controls:

Two control groups, one of 30 healthy controls (Cb), another of 50 COVID-19 survivors without persistent complaints (Ca), matched on age, sex and education with the patient group will be included. The participants for Ca will be recruited in UZA and by advertising. The healthy controls (Cb) will be recruited by mailing within the hospital and by advertising. A positive score on maximum one domain (psychological / cognitive) is allowed in the absence of a psychiatric diagnosis (confirmed by the MINI) and when the complaint causes significant distress (which is investigated during the screening phase).

General exclusion criteria:

Participant is unable to read and understand the consent form and patient-reported outcomes, complete study-related procedures, or communicate with the study staff and informed consent cannot realistically be obtained in retrospect or with the help of a competent family member or legal representative.

Exclusion criteria for each subgroup:

- HPA subgroup
 - Participant is pregnant or breastfeeding
 - Participant receives hormonal replacement therapy (contraception is allowed).
 - Participant is treated with cortisol <4 weeks ago
- Neurocognitive assessment:
 - IQ < 90 (screened with Raven Standard Progressive Matrices (Short Form) (RSPM-SF) (39)
 - Participant takes sedative medication
 - Benzodiazepines: Larger than the equivalent of diazepam 10mg per day. Last administration <8 hours prior to the neurocognitive tests.
 - New sedative antipsychotics/antidepressants (<4 weeks)
 - Other medication from DRUID class III (<4 weeks), last administration <8 hours prior to the neurocognitive tests, or causing significant sedation.

- **Severe** substance abuse (alcohol + drugs)

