Based on current referral rates, we expect on average 1-2 new referrals each week. After 12 months, we expect a total of ± 50 patient inclusions. In a MANOVA analysis, a total sample size of 64 offers 80,0% power to detect a medium sized effect ($f^2 \geq 0.15$). We aim for a total sample size of 130 in order to achieve higher effect sizes and to maintain sufficient power in the subgroup analyses and in case of missing values. As Ca is the main control group for the long COVID patient group, these two groups are of equal size (both 50 participants). We included a smaller Cb group to compare the immunological blood parameters between healthy volunteers and long COVID patients.

Study visits:

As part of routine clinical care, patients will receive psychiatric evaluation at the University Hospital Campus UZA, and neurocognitive evaluation at Campus Duffel. During the clinical evaluations, participants will be invited to participate in the study. If they are interested, they will be invited to a baseline visit assessing eligibility and covering informed consent procedure. In order to adhere to social distancing regulations, it may occur that this baseline visit is held digitally via livestream/webcam or by telephone. In this case, patients sign their ICF digitally. To ensure patient privacy, only in-house fully secured internet and telephone connections will be used for distanced baseline visits.

Once included, the participant will be invited for the baseline assessment, which includes a broad neuropsychological examination. A blood sample will be collected at each time point during the study.

	SCREENING	BASELINE	3 MONTHS	6 MONTHS	12 MONTHS
PATIENT GROUP	Eligibility, psychiatric and IQ screening	Psychiatric assessment Blood sample	Psychiatric assessment Blood sample	Psychiatric assessment Blood sample	Psychiatric assessment Blood sample
+ NC SUBGROUP		Neurocognitive assessment		Neurocognitive assessment	
+ HPA SUBGROUP		Saliva sample		Saliva sample	
CONTROL GROUP A	Eligibility, psychiatric and IQ screening	Psychiatric assessment Blood sample	Psychiatric assessment Blood sample	Psychiatric assessment Blood sample	Psychiatric assessment Blood sample
+ NC SUBGROUP		Neurocognitive assessment			
+ HPA SUBGROUP		Saliva sample			

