3.3.5. Electronic clinical records

The following demographic and clinical variables will be collected through electronic clinical records. If certain data is unavailable from the records, the participant may be contacted by a member of the research team for an additional interview.

- Demographics: age, gender
- Clinical diagnosis at baseline psychiatric evaluation
- Medical history
- Psychiatric history
- Family psychiatric history
- Current + past medication use
- Metabolic parameters: weight, length, waist circumference, triglycerides (TG), HDL-cholesterol, blood pressure, fasting plasma glucose
- Current substance abuse: nicotine, alcohol, cannabis
- If available, results of RT-PCR of SARS-CoV-2 on a nasopharyngeal swab or of SARS-CoV-2 serology
- Date of acute infection, duration of NP symptoms of long Covid
- If available, brain imaging, polysomnography or other technical exams performed during or after COVID-19 infection, including lab results during acute COVID-19 infection
- If available: inflammatory parameters in lab result during acute infection. Otherwise: inflammatory parameters of last clinical lab result (including but not limited to white blood cell count)
- SARS-CoV-2 vaccination status

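### The longitudinal model's covariate rule has no list or limit; read as an inclusion rule, it puts about 25 to 30 nuisance terms into a model for about 50 patients

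*Combined protocol and SAP*

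**What the plan says.** Section 3.5 of the combined protocol and SAP describes one longitudinal analysis. The effect of baseline inflammation and insomnia on neuropsychiatric (NP) symptoms at 3 and 6 months "will be evaluated using linear mixed models with time as repeated effect and patient identifier as within-subject effect", with an unstructured correlation matrix. On adjustment it says two things:

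- "Treatment group (antidepressant treatment, insomnia treatment, cognitive remediation, a combination, or none) will be included" as a predictor, which is a five-category factor.
- "Baseline values of NP symptoms will be included as covariates, and all other covariates measured at baseline as well".

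No section lists the covariates, limits their number, gives a selection rule or says how missing covariate values are handled. Section 3.5 does not name the analysis population either.

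The nearest thing to a list is section 3.3.5: "The following demographic and clinical variables will be collected through electronic clinical records". It runs from demographics through medical history, metabolic measures and substance use to vaccination status. Some entries depend on what the records hold, such as "If available, brain imaging, polysomnography or other technical exams performed during or after COVID-19 infection".

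On numbers, section 3.1 says "The sample size of the patients is estimated on 50 participants". The sample size paragraph says that "a total sample size of 64 offers 80,0% power to detect a medium sized effect", but this is for a MANOVA, not for the mixed model.

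**The concern.** The ordinary reading of the covariate sentence is an instruction to include. Followed as written, it creates two problems.

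1. **Too many terms.** The number of nuisance parameters becomes a large fraction of the number of patients, so the coefficient of interest is estimated with few residual degrees of freedom and an inflated standard error.
2. **Adjustment for near-duplicates.** Nothing keeps other baseline markers or scales out. CRP, IL-6, the systemic immune inflammatory index and the kynurenine metabolites (section 3.4) would adjust for one another. So would HDRS-17 and BDI-21, or ISI and PSQI (Table 1). An IL-6 coefficient conditional on CRP and the index answers a narrower question than whether inflammation predicts symptoms.

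This model carries the longitudinal part of objective 2. A null result from it would say little, because a real association of moderate size could easily be missed.

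**Working it through.** **The plan's own figure.** For a MANOVA global test (Pillai trace), take λ = f²·s·N, df1 = p(g−1), df2 = s(N−g−p+s), with s = min(p, g−1). With f² = 0.15, g = 3 groups, p = 6 responses (assumed: the six cognitive domains) and alpha 0.05 (assumed), N = 64 gives λ = 0.15·2·64 = 19.2, df 12 and 114, and power 80.6%. N = 63 gives 79.8%. The stated 64 is therefore reproducible, but it says nothing about the mixed model.

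**Counting parameters on the inclusion reading.** Section 3.3.5 at one parameter per item:

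- age, gender: 2
- diagnosis, medical history, psychiatric history, family history, medication: 5
- metabolic measures: 7
- nicotine, alcohol, cannabis: 3
- date of infection, duration of symptoms: 2
- vaccination status: 1
- three items recorded only where available (PCR or serology, imaging and other exams, acute inflammatory parameters): 3

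The total is 23, or 20 without the last three. Treatment adds 5 − 1 = 4 and the baseline NP score adds 1. So k = 20 + 4 + 1 = 25, or k = 23 + 4 + 1 = 28. The bio-psycho-social questionnaire in section 3.3 would add about 3 more. Other markers and scales are not counted.

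**Comparator.** A short set of six covariates plus the same 4 df for treatment gives k = 10. The treatment term must be on both sides for a fair comparison.

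**Power.** With complete data, the mixed-model test of a baseline predictor's time-averaged effect equals ordinary regression on each patient's mean. Power is that of a noncentral F with 1 and N − k − 2 df and noncentrality f²·RSSx, averaged over RSSx ~ chi-square(N − 1 − k), for a standardised predictor independent of the covariates.

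At N = 50 and f² = 0.15:

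- k = 10: df2 = 38, mean noncentrality 0.15·39 = 5.85
- k = 28: df2 = 20, mean noncentrality 0.15·21 = 3.15

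The f² of 0.15 is borrowed from the MANOVA statement. A partial correlation of 0.40 (f² = 0.16/0.84 = 0.19) is a second assumed value.

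| k | N = 50, f² = 0.15 | N = 50, r = 0.40 | N = 100, f² = 0.15 |
|---|---|---|---|
| 10 | 64% | 74% | 94% |
| 20 | 51% | 61% | 92% |
| 25 | 44% | 53% | 90% |
| 28 | 39% | 47% | 89% |
| 30 | 36% | 43% | 88% |

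**Precision.** The expected variance of the coefficient is proportional to 1/(N − k − 3). From k = 10 to k = 28 it rises by 37/19 = 1.95, so the standard error is about 1.4 times larger.

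**Sensitivity.** If the extra covariates explain 10% to 30% of the residual variance, power at k = 28 and f² = 0.15 is 42% to 51% instead of 39%.

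**Type I error.** A simulation with no effect, N = 50 and k = 30 rejected in 4.9% of runs, so the test keeps its level.

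**The case against.** **The sentence may only fix timing.** It speaks of covariates, not of all variables, and follows a clause about baseline NP values. Section 3.3.5 never calls its list covariates. On this reading there is no 28-parameter model and no power loss to quantify. This reading is possible, and the conclusion has to be conditional on it. It does not remove the point, because the adjustment set would then be unnamed and could be chosen after the data are seen.

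**A reader might infer that half the attainable power is lost.** The documents do not support that as a headline. A ratio near one half comes from comparing k = 30 with k = 6 (36% against 69% at f² = 0.15), and k = 6 leaves out most or all of the treatment term that any version of the model keeps. Against k = 10 the ratio at k = 28 is about 0.6, and even that depends on assumed values of k, effect size and population.

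**A reader might also infer that fields recorded only where available would remove many patients.** This largely fails. A positive PCR or antibody test is an inclusion criterion for patients. Acute inflammatory parameters have a stated fallback in the same bullet. Imaging and polysomnography date from during or after the infection and are not clearly baseline measures. Section 3.3.5 also allows an interview to fill gaps in the records. The documents give no missing-data rate and do not state complete-case fitting, so no size can be attached. Measures taken only in the neurocognitive and saliva subgroups are a clearer route to lost patients if everything measured at baseline is entered.

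**The aim is exploratory.** Objective 2 is to explore associations, and the test keeps its level. This lowers the severity but does not remove the cost in precision.

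**Conclusion.** The point holds conditionally, as a cheap improvement rather than a defect that must be repaired before the study can be interpreted. Read as an inclusion rule, the sentence in section 3.5 puts about 25 to 30 nuisance parameters into a model for about 50 patients and has related markers and scales adjust for one another. The harm is imprecision, not false positives: power of about 39% instead of 64% (f² = 0.15), or 47% instead of 74% (r = 0.40).

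These figures assume two-sided alpha 0.05 (the plan refers to terms "retained only in models when statistically significant" but states no level), patients only, complete data, k = 28 against k = 10, and extra covariates that are neither prognostic nor related to the predictor. Section 3.5 does not state the population; its treatment term points to patients. With patients and COVID-19 survivors without complaints pooled (N = 100), the loss is only from 94% to 89%. The effect of adjusting for near-duplicate markers and scales was not quantified.

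**What to change.** In section 3.5, delete the second half of the covariate sentence, after the comma, and put in its place:

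- A short prespecified covariate set, identical in every longitudinal model and drawn from data already collected. One example is the outcome's own baseline value, age, sex, BMI (from weight and length), smoking and time since infection, plus the treatment term. The sponsor may prefer other members, such as education, which is a matching factor; what matters is that the list is short and fixed before analysis.
- A statement that other baseline markers, other symptom scales, subgroup-only measures and record fields held only where available are not covariates in the main model.
- The analysis population (patients only, or patients with the COVID-19 survivor controls).
- A rule for missing covariate values.
- Wider adjustment as a labelled sensitivity model.

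The cost is a few sentences of SAP wording and no new data. The downside is that some weak confounders stay unadjusted in the main model; the sensitivity model shows whether that matters.
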